5.6 PHIL PROCEDURE

Unless medically justified, the initial embolization procedure should be performed within 45 days of completion of the baseline assessment. The study procedure consists of pre-placement imaging, study device placement and post-placement imaging. Subjects require no special preparation for the procedure beyond standard of care for endovascular neuro-interventions. Investigators at their discretion may elect to pre-medicate with antiplatelet agents.

It is expected that the majority of PHIL initial and supplemental embolization procedures are completed under general anesthesia but a minority of procedures may be completed under conscious sedation, depending upon the center's standard of care. Heparin is administered according to standard practices. The PHIL device should be used per the IFU provided in the PHIL packaging. The PHIL procedure will be performed only by the physician investigator(s) trained by the Sponsor or its designee to perform the procedure.

The point of enrollment occurs when the PHIL liquid embolic syringe and adaptor assembly is connected to the microcatheter hub.

The investigator will record key characteristics of the device and procedure in the study's eCRF. The investigator will also record technical events/device malfunctions. Radiation exposure will be recorded as absorbed radiation dose and cumulative fluoroscopy time will be recorded. The investigator will retain and provide to the sponsor all images taken during or immediately after the study procedure (including any not specified above).

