5.10 UNSCHEDULED VISIT

Unscheduled visits are those that take place after the study procedure and before the subject completes the study follow-up period (6 months following completion of the last PHIL treatment). Any visit by the subject to the Investigator related to the target dAVF treated or a potentially associated adverse event should include a neurologic examination using mRS, an assessment of dAVF symptoms, and angiography, as per standard of care. The Investigator should document the review of the adverse event status.

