7.1 PROCEDURE FOR ADVERSE EVENT REPORTING

Any medical condition that is present at the time that the subject is screened will be considered part of the subject's baseline medical history and not reported as an adverse event. However, if the subject's condition deteriorates at any time during the study, it may be recorded as an AE. Adverse events will be collected from the point of enrollment in the study until a subject exits the study.

Information to be collected includes event description, time of onset, clinician's assessment of severity, relationship to study product (assessed only by those with the training and authority to make a diagnosis), and time of resolution/stabilization of the event. AEs will be categorized using the definitions in Section 7.2. All AEs collected during the study must be followed by the Investigator until resolution or until the end of the 6 month follow-up. All applicable AEs occurring while on study must be documented appropriately regardless of the relationship.

A list of potential anticipated adverse events is provided in Section 1.3.2. AE reporting responsibilities are described in Section 7.2.

Changes in the severity of an AE will be documented to allow an assessment of the duration of the event at each level of severity to be performed.

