8.2 GENERAL APPROACH

Descriptive statistics (mean, standard deviation, frequency charts, etc.) for baseline participant characteristics, subject disposition and other relevant study parameters will be reported. Where applicable, a comparison to rates reported in the scientific literature will be performed.

Tabulations of summary statistics, graphical presentations, and statistical analyses will be performed using SAS software version 9.2 or higher. The statistical analyses will be based on data pooled across sites in aggregate. All subset summary tables and data listings will be sorted by site and subject. The pre-procedure observations will be used as the baseline value for calculating post-procedural changes from baseline.

Continuous demographic parameters, such as the age of the subject at the time of enrollment, will be summarized using descriptive statistics (N, mean, median, standard deviation, minimum and maximum value). Categorical demographic parameters, such as gender, will be summarized as a proportion of the population.

Data obtained during the neurological examination using the Modified Rankin and self-reported EQ-5D will be summarized at each time point using descriptive statistics.

Routine clinical chemistry and hematology will be assessed by the investigator as normal/abnormal and not clinically significant/clinically significant. The incidence of abnormal and clinically significant values will be summarized and reported in frequency tables for each visit at which the data are collected.

Subject counts will be tabulated for all adverse events for the population. Adverse events will also be tabulated for events that occurred at procedure and at 6 month follow-up after last embolization. Tabulated subject counts will be presented as a proportion of the population.

All recorded data will be presented in the individual data listings.

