## 8. Statistical Analysis Methodology

### 8.1 General Statistical Approach

Descriptive statistics (mean, standard deviation, frequency charts, etc.) for baseline participant characteristics, subject disposition and other relevant study parameters will be reported. Where applicable, a comparison to rates reported in the scientific literature will be performed.

Tabulations of summary statistics, graphical presentations, and statistical analyses will be performed using SAS. The statistical analyses will be based on data pooled across sites in aggregate. All subset summary tables and data listings will be sorted by site and subject. The pre-procedure observations will be used as the baseline value for calculating post-procedural changes from baseline.

Continuous demographic parameters, such as the age of the subject at the time of enrollment, will be summarized using descriptive statistics (N, mean, median, standard deviation, minimum and maximum value). Categorical demographic parameters, such as gender, will be summarized as a proportion of the population.

Data obtained during the neurological examination using the Modified Rankin and self-reported EQ-5D will be summarized at each time point using descriptive statistics.

Routine clinical chemistry and hematology will be assessed by the investigator as normal/abnormal and not clinically significant/clinically significant. The incidence of abnormal and clinically significant values will be summarized and reported in frequency tables for each visit at which the data are collected.

Subject counts will be tabulated for all adverse events for the population. Adverse events will also be tabulated for events that occurred from the start of the procedure to 6 month follow-up after last embolization. Tabulated subject counts will be presented as a proportion of the population.

All recorded data will be presented in the individual data listings.

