#### **8.5 Duration Variables**

Study Day 1 is the day of study device deployment (index procedure). Study day will appear in the listings where applicable and is calculated relative to day 1 using the general formula:

Study Day = (Date of Event – Date of Study Device Deployment) +1, if event date is on or after Date of Study Device Deployment

Study Day = (Date of Event – Date of Study Device Deployment), if event date is before the Date of Study Device Deployment

Duration variables will be calculated using the general formula:

$$[(\text{end date} - \text{start date})] + 1$$

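### SAP 8.1 replaces the protocol's timed adverse-event tabulation with a window that in effect spans the whole collection period, so adverse events of any relatedness are not split by onset

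*SAP*

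**What the plan says.** SAP 8.1 plans two adverse-event tabulations. The first has no time limit: "Subject counts will be tabulated for all adverse events for the population". The second reads: "Adverse events will also be tabulated for events that occurred from the start of the procedure to 6 month follow-up after last embolization". The matching paragraph of protocol 8.2 words the second one differently: "Adverse events will also be tabulated for events that occurred at procedure and at 6 month follow-up after last embolization".

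The collection period is set in protocol 7.1: "Adverse events will be collected from the point of enrollment in the study until a subject exits the study". Protocol 5.6 fixes its start: "The point of enrollment occurs when the PHIL liquid embolic syringe and adaptor assembly is connected to the microcatheter hub". Its end is the planned end of follow-up, which protocol 5.10 places 6 months after the last PHIL treatment. Protocol 7.1 likewise says that adverse events "must be followed by the Investigator until resolution or until the end of the 6 month follow-up".

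For timing in listings, SAP 8.5 says: "Study Day 1 is the day of study device deployment (index procedure"). Protocol 5.8 anticipates as many as seven PHIL procedures for one fistula, and protocol 15 defines the procedure as the index one.

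SAP section 3 describes the SAP as a supplement to the protocol. The SAP revision history, up to Revision B of 21 February 2023, does not mention a change to this tabulation. Protocol Revision E is dated 3 April 2023, so the two-time-point wording stands in the later document.

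**The concern.** The second tabulation is introduced as an addition to the first, and in the protocol it is one: it picks out events at the procedure. If the SAP window holds the same events as the all-event table, it adds nothing, and a team that follows the SAP will not produce the at-procedure tabulation that the current protocol specifies.

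The study is single-arm and open-label, and describing safety is half of its stated objective. Without a control group, a reader judges whether an event follows treatment partly by how soon after a procedure it began. That information does not depend on anyone's view of cause. If adverse events are placed in time only after being classed as related to the device or procedure, then events classed as due to the study disease, a concomitant disease or an unknown cause have no place in time in any table. Repeat procedures add to the difficulty, because a single clock from the index procedure does not show how close an event was to a later one.

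**Working it through.** The plan gives no figure for this point, so the check is mainly a comparison of texts.

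**Step 1. SAP window against collection period.**
- Start: the SAP window opens at the start of the procedure. Collection opens at enrollment, when the syringe assembly is connected to the microcatheter during that procedure (protocol 5.6, 7.1). The window therefore opens at or before collection, and no collected event is excluded at the front.
- End: the window closes at the 6-month follow-up after the last embolization. Collection closes at study exit, planned at the same visit (protocol 5.10, 5.15). For a subject who leaves early, collection stops at exit, so both tables hold the same events.
- Possible difference: the 6-month visit may fall up to 6 weeks late (protocol 5.9.3), or 20 weeks late under the COVID-19 provision (protocol 5.12). If the SAP window were cut at a fixed 6-month date instead of at the visit, events in that tail would appear only in the first table. Nothing else separates the two.

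Result: the second tabulation in effect equals the first.

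**Step 2. What the SAP keeps near a procedure (SAP 8.2, 8.3).**

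| Summary | Time reference | Restricted by |
|---|---|---|
| Neurological death or ipsilateral stroke, primary | 30 days after first PHIL procedure | these two events |
| Neurological death or ipsilateral stroke, secondary | 30 days after all PHIL treatments | these two events |
| Device-related adverse events | procedure and 30 days | relatedness |
| Device-related mortality | procedure and 30 days | relatedness |
| Procedure-related adverse events | no window stated; the definition in protocol 7.2.1 requires closeness in time to any PHIL procedure | relatedness |
| Clinically significant technical events | during the procedure(s) | event type |

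Of the six, two need no relatedness call but cover only two kinds of event, three depend on relatedness, and one depends on event type. New intracranial hemorrhage and cranial nerve palsy are counted without a relatedness condition, but at 6 months and not by onset. The number of tables giving adverse events of any relatedness by time of onset is 0.

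**Step 3. What the listings show.** SAP 8.5 gives Study Day = (event date − index date) + 1. For an event k days after a supplemental procedure that was itself done d days after the index, Study Day = d + k + 1. The documents give no value for d. Expected participation is up to 9 months, of which 6 are follow-up, so 9 − 6 = 3 months remain for baseline and all treatment. Taking assumed gaps of 30, 60 and 90 days with k = 1:
- d = 30: 30 + 1 + 1 = 32
- d = 60: 60 + 1 + 1 = 62
- d = 90: 90 + 1 + 1 = 92

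In each case the event began 1 day after the most recent PHIL procedure, and Study Day alone does not show it.

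**The case against.** The strongest reply is that the SAP already describes peri-procedural harm. A reader might infer from the duplicated window that no table shows which events cluster around a PHIL procedure. That goes too far, as the six summaries in Step 2 show. The most serious acute neurological events have 30-day counts with confidence limits and no device- or procedure-relatedness condition, and procedure-related events are by definition close in time to any PHIL procedure, supplemental ones included. Nor does relatedness necessarily rest on the treating investigator alone, because protocol 7.4 has primary and secondary outcomes adjudicated by at least three independent physicians. All of this stands. It leaves open the adverse events that are neither stroke nor neurological death and are not classed as device-related, procedure-related or technical.

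A reader might also take SAP 8.5 to be the only clock in the SAP. It is not: SAP 8.2 and 8.3 count from completion of the first procedure and of all treatments. Study Day is a listing variable and governs no table. Since all recorded data are to be listed, time from a later procedure could be worked out by hand if the procedure dates appear there. That softens the point about listings but does not supply a pre-specified table.

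A third inference would be that 12–48% of subjects will need repeat procedures, from 100 − 88 and 100 − 52 in protocol Table 3. Those shares come from Onyx and nBCA series, not PHIL, and some of those patients also received coils, surgery or radiosurgery. They cannot be used as a figure for this trial.

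Finally, protocol 8.2 names two time points without promising separate tables, and its reference to the 6-month follow-up could mean events present at that visit or cumulative to it. With the protocol's definition of procedure as the index one, merely restoring its wording would not bring in supplemental procedures. This is fair. Counting from the most recent procedure is a recommendation that goes beyond what the protocol states.

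**Conclusion.** The point holds in a limited form. SAP 8.1 departs from the current protocol without saying so, and its second adverse-event tabulation in effect repeats its first. Apart from 30-day neurological death or ipsilateral stroke, the remaining peri-procedural summaries depend on a relatedness or event-type classification, and adverse events of any relatedness are not split by onset in any table that the SAP describes.

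The consequence is modest. The study is descriptive, no primary or secondary outcome is affected, and a redundant table does not mislead. What is lost is one specified tabulation and a view of timing that does not depend on judged cause. The size in terms of events cannot be stated from the documents, and the gaps in Step 3 are illustrations only. The conclusion assumes that the 6-month follow-up in the SAP window means the 6-month visit; a fixed date would change only the late tail. The correction should be made because it is cheap and serves the study's own safety objective.

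**What to change.** - **SAP 8.1.** Replace the second tabulation with subject counts of adverse events and of serious adverse events, of any relatedness, by onset since the most recent PHIL procedure: from the procedure to discharge; after discharge to day 30; after day 30 to the 6-month visit. Count a subject once per interval and state the denominator.
- **SAP 8.5.** Derive days since the most recent PHIL procedure as event date minus the date of the latest PHIL procedure at or before onset, state the day-numbering convention, and list it beside Study Day.
- **Protocol 8.2.** Say whether the 6-month entry is cumulative or means events present at the visit, and whether the at-procedure entry includes supplemental procedures, so that both documents describe the same tabulation. If the protocol is not amended, record the difference in the clinical study report, as SAP section 3 provides.

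The cost is SAP wording, one derived variable and one table split. Time of onset is already collected (protocol 7.1), and sites must keep the date and time of each device use (protocol 12.2). Confirm that supplemental procedure dates are in the eCRF data alongside the procedure characteristics that protocol 5.8 requires. No new assessment is needed and no clinical rule is touched.

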### **6. Determination of Sample Size**

This study will enroll up to seventy five (75) subjects in this study to obtain 6 month follow-up in 60 subjects. This assumes up to fifteen (15) subjects may be lost to follow-up. No statistical justification is established.

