### **7. Study Subjects**

#### **Analysis Population**

The analysis population will be comprised of the results from up to 75 treated subjects. Results will be presented based on one population:

Full Analysis Set (FAS): defined all enrolled subjects in whom the PHIL device was implanted.

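### The general adverse-event tables in SAP 8.1 use the whole FAS as denominator with no allowance for time at risk, so late-onset AE rates can only be understated or unaffected

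*SAP*

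**What the plan says.** SAP 8.1 sets the rule for the general AE tables. On the window: "Adverse events will also be tabulated for events that occurred from the start of the procedure to 6 month follow-up after last embolization". On the denominator: "Tabulated subject counts will be presented as a proportion of the population". Protocol 8.2 has the same denominator rule.

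SAP 7 gives one population: "Full Analysis Set (FAS): defined all enrolled subjects in whom the PHIL device was implanted". Its size is up to 75.

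Protocol 7.1 limits collection: "Adverse events will be collected from the point of enrollment in the study until a subject exits the study". Under Protocol 4.4.1, data recorded before a withdrawal are kept and analysed.

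SAP 6 sets the size: "This study will enroll up to seventy five (75) subjects in this study to obtain 6 month follow-up in 60 subjects". It adds: "This assumes up to fifteen (15) subjects may be lost to follow-up".

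The named safety outcomes are treated differently. SAP 8.2 and 8.3 report the primary and secondary outcomes over the number of subjects evaluated, with Clopper-Pearson limits, and SAP 8.6 adds a sensitivity analysis on imputed data. SAP 8.6 covers primary and secondary outcomes only. Neither document plans a censored, person-time or number-at-risk summary for the general AE tables.

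**The concern.** A subject lost at week 6 counts in the denominator for the full window, but nothing that happens to that subject afterwards can be recorded. In the table, that subject is indistinguishable from one followed to 6 months without an event.

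At stake are the results that only these tables carry:

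- AEs and SAEs overall up to 6 months;
- all-cause death;
- device-related AEs and device-related deaths after 30 days, since SAP 8.3 stops at 30 days for both;
- strokes after 30 days that do not also count as intracranial hemorrhage, permanent morbidity or an unresolved device- or procedure-related neurological event.

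SAP 8.1 also foresees comparison with literature rates where applicable. Some benchmarks in Protocol 1.2.4 and 7 are annual (8.1% hemorrhage, 6.9% non-hemorrhagic deficit, 15% combined), and a proportion without time at risk is hard to set against an annual rate.

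**Working it through.** **1. The plan's own figure.** A follow-up target of 60 and a loss allowance of 15/75 = 20% give 60 / (1 − 0.20) = 75. The enrolment figure reproduces.

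**2. Direction.** Take the 75 subjects as given. Events recorded before exit are a subset of the events that full follow-up would have recorded, and the denominator is 75 in both cases. The tabulated proportion therefore cannot exceed the full-follow-up proportion. This needs no assumption about why subjects leave.

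**3. Size.** The documents give no late-event risk, so I assume values of 5%, 10% and 20%. Let p be the risk of a late event over 6 months, with a constant hazard, 15 uninformative losses, and each lost subject leaving at fraction f of the 6 months.

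- Chance that a lost subject's event is recorded: 1 − (1 − p)^f
- Table shows: [60p + 15 × (1 − (1 − p)^f)] / 75
- For losses spread evenly, replace the bracket for lost subjects by its average over f, which is 1 − p/h with h = −ln(1 − p)

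For p = 10%:

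- lost at the start: (6 + 0) / 75 = 8.0%
- lost at 1 month: (6 + 15 × 0.0174) / 75 = 8.3%
- lost evenly: (6 + 15 × 0.0509) / 75 = 9.0%
- lost at month 5: (6 + 15 × 0.0841) / 75 = 9.7%

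| All 15 lost | p = 5% | p = 10% | p = 20% | Share of p shown |
|---|---|---|---|---|
| at the start | 4.0% | 8.0% | 16.0% | 0.80 |
| at 1 month | 4.2% | 8.3% | 16.7% | 0.83–0.84 |
| evenly over time | 4.5% | 9.0% | 18.1% | 0.90 |
| at month 5 | 4.8% | 9.7% | 19.4% | 0.97 |

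**4. Dilution by early events.** Assume 10% of subjects have an event at or near the procedure, and 5% of the rest have a late one. The full-follow-up figure is 0.10 + 0.90 × 0.05 = 14.5%. With all 15 lost straight after the procedure, the table shows 0.10 + 0.90 × 0.05 × 0.80 = 13.6%, a ratio of 0.94. With the even-loss factor it shows 0.10 + 0.90 × 0.05 × 0.90 = 14.05%, a ratio of 0.97.

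**5. Against sampling error.** Six subjects with an event give 6/75 = 8.0% (Clopper-Pearson 95% interval 3.0% to 16.6%). Over the 60 followed subjects they give 6/60 = 10.0% (3.8% to 20.5%).

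**The case against.** The strongest reply is that the results that matter most are protected. New intracranial hemorrhage, new cranial nerve palsy, permanent morbidity and unresolved device- or procedure-related neurological events at 6 months are secondary outcomes in SAP 8.3. They are reported over the number evaluated, and SAP 8.6 gives them imputation and a tipping-point analysis. The primary safety outcome ends at 30 days. A reader might infer from SAP 8.1 that the main safety results are understated. The documents do not support that, and this objection stands in full.

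Second, 15 is a planning ceiling: the SAP says up to 15 may be lost. Reading it as the expected loss goes too far, so every figure above is an upper case on the number lost. Early disappearance of all 15 is also unlikely under the protocol. Enrolment takes place at the procedure, a discharge examination follows, missed visits prompt contact, and loss is declared only after three attempts. This stands too.

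Third, the study is descriptive, with no control arm and no threshold (SAP 6: "No statistical justification is established"). Protocol Table 5 itself lists event counts beside N, which crude counts match. A shift of 1 or 2 points is small beside the interval in step 5. This limits the importance of the point, but sampling error does not cancel an error whose only possible direction is downward.

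Fourth, disposition and individual listings are reported, with study day where applicable. They would let a reader rebuild the time at risk, but they are not a summary of it.

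**Conclusion.** The point holds for the general AE and SAE tables of SAP 8.1 only. Their late-event rates will be understated or unaffected. With all 15 allowed losses, uninformative loss and a constant hazard, they show between 0.80 and 0.97 of the late-event risk, and about 0.90 if losses are even over time. Fewer losses shrink the gap; losses linked to coming events could widen it beyond a fifth. The late risks of 5% to 20% are assumptions.

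A reader might go further and conclude that the tables are certain to favour the device. The documents do not support this. The gap may be negligible, and with no control arm any advantage concerns only the absolute rate or a literature comparison; the documents do not say whether the literature rates are themselves crude. This is a worthwhile improvement, and no planned primary or secondary result depends on it.

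**What to change.** Keep the crude counts in SAP 8.1 and add one table covering any SAE, all-cause death, stroke, and device- or procedure-related AEs. Specify:

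- **Time origin:** the index procedure, Study Day 1 in SAP 8.5. It must be stated because the AE window in SAP 8.1 ends 6 months after the last embolization, and Protocol 5.8 foresees up to seven procedures. Events beyond 6 months from the index procedure stay in the crude counts.
- **Estimate:** cumulative incidence at 30 days and 6 months, with subjects censored at study exit. Use Kaplan-Meier for all-cause death, and treat death as a competing event for the non-fatal events.
- **Number at risk** at both times. The 6-month visit may take place up to 3 weeks early (Protocol 5.9.3), so some subjects who complete the study will be censored just before the 6-month mark.
- **A note** that censoring at exit assumes uninformative loss, and that SAP 8.3 remains the source for the secondary outcomes.

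The cost is one extra table from event-onset and exit data already recorded. Late-event rates would be slightly higher than the crude figures: at a late risk of 10%, by about 1 point (10.0% against 9.0%) if all 15 are lost evenly and 2 points (10.0% against 8.0%) if all are lost at the start. Some events will also appear under two differently defined rates, so the table footnotes should say which is which.
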